6.2. Study Period

6.2.1. Baseline Visit (Randomization)

- Assess baseline symptoms by spontaneous reporting of symptoms and by asking the subjects to respond to a non-leading question such as “How do you feel?” Record adverse events;
- Record height and weight and orthostatic vital signs (sitting, supine, and standing);
- Have Subject self-administer the HADS ([Appendix 3](#));
- Conduct Neuropsychiatric Adverse Event Interview (NAEI) ([Appendix 4](#)) and record solicited adverse events;
- Complete the Columbia Suicide-Severity Rating Scale (C-SSRS) and record any suicide-related adverse events;
- Collect urine for **pregnancy** test from females;
- Perform urine **drug** test on all subjects;
- Urine cotinine at site;
- Record concomitant medications;
- Record any non-drug treatments/procedures;
- Review previous week’s Smoking Diary Worksheet with subject and distribute the following week’s; Complete the Nicotine Use Inventory (NUI) based on subject responses ([Appendix 1](#));

- Provide up to 10 minutes of smoking cessation counseling;
- Re-check [Inclusion Criteria/Exclusion Criteria](#);
- Randomize to treatment;
- Dispense study medication, Week 1 blister pack, for self administration and provide dosing instructions.

6.2.2. Treatment Phase Clinic Visits (Weeks 1 through 12 and ET₁₂)

Following the Baseline visit, clinic visits will be conducted weekly for 12 weeks. All subjects should have set a target quit date (TQD) to coincide with the Week 1 visit. The Week 1 visit occurs at the end of the first week of the treatment phase. Smoking cessation counseling up to 10 minutes duration will be provided at each clinic visit beginning at Baseline. Whenever possible, counseling should be conducted by the same counselor throughout, so that the relationship builds and brings additional value to the sessions. Every effort should be made to have the subject return on the same day of the week for the clinic visits, thereby keeping visits on time. To accommodate unforeseen circumstances a visit window of ± 3 days can be allowed as long as proper dosing is maintained. If an early termination occurs before the end of Week 12, an early termination visit (ET₁₂) will be conducted. At each of these visits, the following procedures will be conducted:

- Record spontaneously reported adverse events after asking the subjects to respond to a non-leading question such as “How do you feel?”
- Measure and record sitting and orthostatic blood pressure (BP) and sitting, supine and standing pulse rate;
- Have Subject self-administer the HADS ([Appendix 3](#));
- Conduct Neuropsychiatric Adverse Event Interview (NAEI) ([Appendix 4](#)) and record solicited adverse events;
- Complete the Columbia Suicide-Severity Rating Scale (C-SSRS) and record any suicide-related adverse events;
- Record concomitant medications;
- Record any non-drug treatments;
- Review previous week’s Smoking Diary Worksheet with subject and distribute the following week’s; Complete the Nicotine Use Inventory (NUI) based on subject responses ([Appendix 1](#));
- Provide up to 10 minutes of smoking cessation counseling;

- Count and document drug returns;
- Dispense next week's blister pack (except at Week 12 or ET);

The following additional activities will be conducted at Visit Weeks **3, 6, 12**, and early termination:

- Obtain blood samples for safety laboratory tests (week 3, Week 6, and Week 12 or ET);
- Perform urine **pregnancy** test for females (also at **Week 9**);
- Perform urine **drug** test (dipstick at site) (also at **Week 9**);
- Collect blood samples for pharmacokinetic analysis (Week 3, Week 6, and Week 12 or ET);
- Ask subject to recall the times of last 2 doses of trial medications and record this information in the dosing log;
- At Week 12 or ET12 only, record height and weight;

The following additional activity will be conducted at Visit Weeks 9-12, and at Early Termination:

- Urine cotinine test at site;

6.3. Non-Treatment Follow-up Period (Weeks 13-52)

Following completion of the week 12 visit, subjects will continue in the non-treatment follow-up phase of the protocol. Clinic visits occur weeks 13-16, 20, 28, 36, 44, and 52/ET. Subjects will be contacted by phone at weeks 24, 32, 40, and 48. During the non-treatment phase, smoking cessation counseling up to 10 minutes duration will be provided at each visit and telephone contact. To accommodate unforeseen circumstances, a visit window of ± 3 days can be allowed for weeks 13 through 20 visits, and a visit window of +5 days can be allowed for week 20 to week 52 visits.

6.3.1. Clinic Visits: Weeks 13-16, 20, 28, 36, 44, and 52/ET

- Record spontaneously reported adverse events by asking the subjects to respond to a non-leading question such as "How do you feel?"
- Subject self administers the HADS ([Appendix 3](#));
- Conduct Neuropsychiatric Adverse Event Interview (NAEI) ([Appendix 4](#)) and record solicited adverse events;

- Complete the Columbia Suicide-Severity Rating Scale (C-SSRS) and record any suicide-related adverse events;
- Record concomitant medications;
- Record any non-drug treatments;
- Review previous week's Smoking Diary Worksheet with subject and distribute the following week(s); Complete the Nicotine Use Inventory (NUI) based on subject responses ([Appendix 1](#));
- Urine cotinine test at site;
- Provide up to 10 minutes of smoking cessation counseling.

6.3.2. Telephone Contacts: Weeks 24, 32, 40, and 48

- Review Smoking Diary responses with subject;
- Complete the Nicotine Use Inventory (NUI) based on subject responses ([Appendix 1](#));
- Provide up to 10 minutes of smoking cessation counseling.

Discharge from study at Week 52 or early termination only. If a subject has any clinically significant and trial-related abnormalities at the conclusion of a scheduled visit of the trial, the Pfizer medical monitor (or designated representative) should be notified and the follow-up evaluations will be performed until the abnormalities return to the normal/baseline condition. The investigator should make every effort to arrange follow-up evaluations at appropriate intervals to document the course of the abnormalities.

6.4. Early Permanent Discontinuation of Study Drug

Subjects who wish to withdraw from the study will be allowed to do so at any time without prejudice, or they may be withdrawn at any time at the discretion of the investigator or sponsor for safety or behavioral, or the inability of the subject to comply with the protocol required schedule of study visits or procedures at a given study site. Subjects should be discontinued if they cannot be contacted for drug monitoring or do not return for subsequent scheduled visits. The investigator should inquire about the reason for withdrawal, request the subject to return all unused investigational product(s), request the subject return for a final visit, if applicable and follow-up with the subject regarding any unresolved adverse events (AEs). Diligent attempts will be made by telephone and certified letter to determine the circumstances for subjects who are lost to follow-up as this may be related to the study drug.

Early permanent withdrawal of study drug use may occur at any phase of the study. Possible reasons for early permanent withdrawal of study drug use include:

- Adverse event: The subject develops an adverse event, which in the opinion of the subject or lead investigator, institutional principal investigator or sub-investigator warrants termination of study drug use.
- Personal reason: A subject may withdraw from study drug use at any time.
- Pregnancy.

In the event of study treatment discontinuation, subjects should be encouraged to continue to attend clinic and telephone visits, and complete study procedures.

The investigator must determine the primary reason for withdrawal of study drug and record it on the case report form. Withdrawal of study drug due to an adverse event should be distinguished from withdrawal of study drug due to insufficient response. A treatment or study discontinuation due to a serious adverse event must be reported to Pfizer immediately.

Return to smoking is not a basis for withdrawing a subject from the study. Subjects who return to smoking should be encouraged to make further quit attempts and to continue their participation with the counseling and protocol-specified visits and procedures.

Female subjects who have a positive pregnancy test during the treatment period will discontinue study medication but should continue study participation. Pregnant subjects must be followed to the outcome of the pregnancy and an Exposure in Utero Form (EIU) must be submitted.

Any subjects who discontinue treatment for any reason may continue participation in the study and should be encouraged to do so. They will be required to maintain the visit schedule and can continue participation through the non-treatment follow-up phase of the study.

Subjects should be encouraged to complete the study even if they stop study medication. If the subject withdraws from the study, and also withdraws consent for disclosure of future information, no further evaluations should be performed, and no additional data should be collected. The sponsor may retain and continue to use any data collected before such withdrawal of consent.

In post marketing safety surveillance there have been some reports of depressed mood, agitation, changes in behavior, psychosis, hallucinations, paranoia, delusions, homicidal ideation, hostility, anxiety, panic, and suicidal ideation (suicidal thoughts) and suicide in patients attempting to quit smoking while taking varenicline. Because these events are reported voluntarily from a population of uncertain size, it is not always possible to reliably estimate their frequency or establish causal relationship to drug exposure. The role of varenicline in these reports is not known. A subject who experiences such events should stop dosing and immediately report any such symptoms to the study staff.

Each clinical research site will have an Emergency Response Plan in place to properly care for subjects who report events of a serious nature that require immediate or very

prompt attention. This plan will include having a pediatric/adolescent psychiatrist available at all times.

At all clinic visits, the investigator will be proactively monitoring for anxiety, panic, hostility, aggression, abnormal thinking, hallucinations, suicidality and depressed mood through the use of the C-SSRS, HADS ([Appendix 3](#)), and the NAEI ([Appendix 4](#)). These evaluations should be conducted by an adolescent or pediatric psychiatrist. A subject must be discontinued from study medication and referred for appropriate medical or psychiatric evaluation and follow-up if there is:

- A positive response to any question on the C-SSRS;
- A score ≥ 15 for anxiety or >15 for depression on the HADS ([Appendix 3](#));
- Moderate or severe adverse event as elicited through the use of the Neuropsychiatric Adverse Event Interview.

Subjects may withdraw from the study at any time at their own request, or they may be withdrawn at any time at the discretion of the investigator or sponsor for safety, behavioural, or administrative reasons. If a subject does not return for a scheduled visit, every effort should be made to contact the subject. In any circumstance, every effort should be made to document subject outcome, if possible. The investigator should inquire about the reason for withdrawal, request the subject to return all unused investigational product(s), request the subject return for a final visit, if applicable, and follow-up with the subject regarding any unresolved adverse events.

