4.2. Exclusion Criteria

Subjects presenting with any of the following **will not** be included in the study:

1. Female subjects with a positive urine pregnancy test (all female subjects are required to have pregnancy testing).
2. Pregnant or nursing female subjects; females of childbearing potential who are unwilling or unable to use an acceptable method of contraception from at least 14 days prior to study medication administration until 30 days after the last dose of study medication. Acceptable methods of contraception are: abstinence; any form of hormonal contraception such as Depo-Provera, daily oral contraceptive, transdermal patch, or Nuva-ring; intra-uterine device, sterilization; or double barrier contraception which is a combination of any two of the following methods: condoms, spermicide, diaphragm. (Note, subjects with a positive pregnancy test during the treatment period will have study drug discontinued but will be encouraged to remain in the study).
3. Subjects with a prior suicide attempt, subjects hospitalized within the past twelve months due to suicidal ideation or suicidal behavior, or subjects considered to have had serious suicidal ideation or suicidal behavior within the past twelve months.
4. Subjects with active suicidal ideation or behavior identified at the screening or baseline visits.
5. Subjects with a score of >7 on the Suicide Behaviors Questionnaire-Revised (SBQ-R) at the Screening visit.
6. Subjects with current evidence or history of clinically significant psychiatric disease, including, but not limited to Axis 2 disorders; major depression disorder, anxiety disorders, panic disorder, hostility or aggression disorder, perceptual/thinking disturbances, mania, psychosis, (including schizophrenia), bipolar disorder, personality disorder, severe emotional problems (in the past year prior to screening), or eating disorder (eg, bulimia or anorexia nervosa). Investigator judgment should be used to assess whether a prospective subject is appropriate for participation in the study.

Assessment of any evidence or history of clinically significant psychiatric or neurologic disease, and the assessment for suicidality must be done by a Mental Health Professional (MHP). A MHP must be a pediatric/adolescent psychiatrist or a licensed PhD level clinical pediatric/adolescent psychologist.

7. Subjects who require use of medications prescribed for mania or psychosis.

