4.3. Randomization Criteria

Subjects who meet inclusion and exclusion criteria and have no clinically significant abnormalities on laboratory test results or physical examination may be randomized. A computer-generated randomization schedule will be used to assign subjects to treatment.

[figure not shown]

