7.2.5. Columbia Suicide Severity Rating Scale (CSSRS)

The Columbia suicide Severity Rating Scale (CSSRS)¹⁶ is a set of suggested questions designed to elicit information about passive and active suicidal ideation, active suicidal intent, and self injurious behavior.

The C-SSRS will be completed by a mental health professional (adolescent psychiatrist or PhD psychologist), at screening and at each subsequent clinic visit up to and including Week 52.

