9.2. Safety Analysis

All safety analyses will be performed overall as well as on the subgroup of patients who are 12-16 years of age. Laboratory and other safety data will be subjected to clinical review and summarized, using Pfizer Data Standards, by frequencies of events and mean changes from Baseline.

The following summaries will be used to assess the safety of subjects in this study:

- Incidence and type of AEs;
- Incidence and type of SAEs;
- Change from baseline in laboratory parameters;
- Incidence of clinically significant laboratory parameters;
- Change from baseline in vital signs;
- Incidence of clinically significant vital sign parameters;
- Frequency and percent of subjects endorsing suicidal ideation or behavior.

All safety analyses will use the population of all subjects who received at least 1 dose of study drug.

In addition to the standard safety summaries for the vital signs data collected at each visit, the change from Baseline in BMI at Week 12 will be summarized by treatment group. Change from Baseline in BMI and any other safety endpoints of interest may be summarized for subgroups of interest if the number of subjects in the subgroup permits.

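### SAP 8.2.6.8 labels C-SSRS responses treatment emergent by date alone, and no planned table compares them with the subject's own baseline

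*Protocol*

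**What the plan says.** **Collection.** The C-SSRS is completed at screening and at every later clinic visit (Protocol 7.2.5). At the randomization visit the site must "Complete the Columbia Suicide-Severity Rating Scale (C-SSRS) and record any suicide-related adverse events" (Protocol 6.2.1). Dosing starts no earlier than the next morning (Protocol 5.6), so each dosed subject should have a pre-dose answer.

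**Stopping.** Protocol 6.4 requires study drug to stop and the subject to be referred after "A positive response to any question on the C-SSRS".

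**Protocol summary.** Protocol 9.2 lists "Frequency and percent of subjects endorsing suicidal ideation or behavior" among the safety summaries.

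**SAP summary.** SAP 8.2.6.8 tabulates C-CASA categories by arm for four periods: lifetime at screening, baseline, treatment emergent and follow-up. The treatment-emergent period runs from first dose to 30 days after last dose. A later visit also counts if its since-last-visit recall interval contains the end of that window. Listings carry the observed C-SSRS data and the C-CASA categories.

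**Comparator in the same SAP.** For the HADS, SAP 8.2.6.7 plans a shift from each subject's baseline category to their worst later category, and counts subjects who moved up.

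**The concern.** A reader of a safety table takes treatment emergent to mean new or worse since treatment began. The SAP's C-SSRS definition does not require that. A subject who reported passive ideation before the first dose, and reports the same at Week 1, is counted as treatment emergent.

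The baseline row does not resolve this. It gives an arm total, and a total cannot show whether the people in it are also in the treatment-emergent row. If any subject is positive before dosing, the planned tables cannot separate ideation that arose or worsened on drug from ideation that was already there. Protocol 1.2 calls the trial a post-authorization safety study, and Protocol 3 gives monitoring for suicide-related events as a purpose of follow-up, so the distinction is worth having in a prespecified table.

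**Working it through.** There is no planned figure to reproduce. The check compares the texts and then gives a scale.

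**1. Does any part of the rule refer to baseline?** The main window is set by the dates of first and last dose. The look-back rule is also a date rule: it extends the window. Neither looks at the subject's pre-dose answer.

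**2. Can the planned rows recover the answer?** Take an arm of n subjects, with k positive at baseline and m positive in the treatment-emergent period. The number positive in both can be anything from max(0, k + m − n) to min(k, m). With n = 100 and k = m = 1, the overlap is 0 or 1:

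| Case | Baseline row | Treatment-emergent row | New or worse |
|---|---|---|---|
| Two different subjects | 1/100 | 1/100 | 1 |
| Same subject, response worse | 1/100 | 1/100 | 1 |
| Same subject, response no worse | 1/100 | 1/100 | 0 |

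If the category is the same, the first and third cases give identical rows with different meanings. A change of category in the second case could show in the category counts, but the rows would still not show that it was the same person. If k = 0 there is nothing to separate.

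**3. Could k exceed zero?** The documents give no rate. Exclusions 3 to 6 and 8 (Protocol 4.2) make it unlikely. If such a subject is dosed, however, SAP 5.3 keeps everyone who took a dose in the safety set, and SAP 5.5 does not remove subjects for eligibility violations.

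**4. Scale per subject.** Protocol 9.1 plans 100 subjects per arm, and about 70 per arm aged 12-16. One subject whose response is no worse than baseline adds:
- Overall: 1/100 = 1.0 percentage point.
- 12-16 stratum: 1/70 = 1.4 percentage points.

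This is a conversion, not an estimate of how many subjects there are.

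**5. Is the comparison feasible?** SAP 6.3 defines baseline as the last evaluation before first dose, and the C-SSRS is done at the baseline visit. The inputs exist.

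**The case against.** The case against has real weight.

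- **Listings.** The same SAP section provides subject-level listings. With about 300 subjects and few positives, a reviewer could trace each one. This stands and limits the consequence. But manual tracing is not a prespecified summary by arm.
- **Protocol 9.2 is met.** It asks only for "Frequency and percent of subjects endorsing suicidal ideation or behavior", and the SAP delivers that. It would be wrong to infer that the SAP breaks a protocol commitment.
- **Nothing is pooled or recounted.** A reader might infer that baseline or lifetime responses leak into the treatment-emergent row. They do not: they have their own rows, and the SAP describes a since-last-visit administration.
- **Counting everything is cautious.** This is true of the total, which should stay. It does not answer how much of the total is new.
- **Adverse event tables exist.** Suicidal ideation and behavior terms are summarized separately (SAP 8.2.6.1, Appendix 1). Those tables rest on recorded adverse events and do not compare C-SSRS responses with baseline.
- **The HADS is a scored scale.** A shift table is more natural there, but ordered C-SSRS categories can be compared in the same way.

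A stronger reading is also tempting. Exclusion 4 bars "Subjects with active suicidal ideation or behavior identified at the screening or baseline visits" without defining active, and Protocol 7.2.5 describes the scale as "designed to elicit information about passive and active suicidal ideation". A reader might infer that a passive-only positive subject may be randomized and then stopped a week later. The documents do not support that as a fault. Exclusion 3 deals with history ("subjects considered to have had serious suicidal ideation or suicidal behavior within the past twelve months"), so active most naturally means current. The protocol says "the assessment for suicidality must be done by a Mental Health Professional (MHP"), sends doubtful cases to the sponsor (Protocol 4), and lists a re-check of the criteria after the baseline C-SSRS (Protocol 6.2.1). A stop rule stricter than the entry rule is cautious, not inconsistent. Defining the word would be an optional clarification.

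**Conclusion.** The point holds for the analysis plan only. SAP 8.2.6.8 defines treatment-emergent C-SSRS responses by date, so a response no worse than the subject's pre-dose baseline takes that label, and no planned table links the two within subject. The HADS has that link and the C-SSRS does not.

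The size is unknown and may be zero. It depends on how many subjects are positive before dosing and report the same again, which the documents do not give. The per-subject figures of 1.0 and 1.4 percentage points assume the planned arm sizes. They say nothing about bias between arms. Efficacy inference is untouched. This is a low-priority improvement with almost no cost.

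**What to change.** In SAP 8.2.6.8, keep the on-treatment total and the look-back rule. Add a within-subject summary by arm, for the groups already listed there, with two lines:

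1. Subjects whose treatment-emergent response is new, or more severe than their own pre-dose baseline (SAP 6.3 definition).
2. Subjects whose response persists from baseline without worsening.

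State the category order used for more severe, and show separately any subject without a pre-dose assessment.

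Leave the Protocol 6.4 stop rule as it is. The cost is a short SAP addition and two table lines from data already collected, with no new visits or assessments. It can be made at any time before database release, when SAP 3 has the final analysis first run. If no subject is positive at baseline, the second line will be empty, and the table will show that directly.

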8. Subjects with a score ≥ 8 for *either* depression or anxiety on the Hospital Anxiety and Depression Rating Scale (HADS) ([Appendix 3](#)).
9. Subjects with evidence or history of clinically significant neurological, hematological, renal, endocrine, pulmonary, gastrointestinal, cardiovascular, hepatic, or allergic disease (including serious drug allergies). (Subjects who have seasonal allergies, asthma, or acne may be allowed to enroll in the study).
10. Use of prescription or nonprescription drugs within 7 days or 5 half-lives (whichever is longer) prior to the first dose of study medication should be discussed with the sponsor and recorded on the CRF. Use of ibuprofen, acetaminophen at doses of ≤ 2 g/day, antihistamines, asthma medications, bronchodilators, migraine medications and topical medications is permitted.
11. Use of psychotropic or psychoactive drugs in the 6 months prior to screening should be discussed with the sponsor prior to enrolling the subject. Use of Adderal or Ritalin may be allowed for treatment of those subjects with ADHD who are otherwise deemed appropriate for this study.
12. Evidence of alcohol and substance abuse/dependence (other than nicotine) within 3 months prior to screening deemed severe enough to compromise the subject's ability to comply with the study requirements, as determined by the investigator's clinical judgment, OR consecutive positive urine drug screens during **screening and baseline**. If question remains as to the suitability of the subject, contact the sponsor, or use DSM IV guidance to assess potential for substance abuse.
13. Treatment with an investigational drug within 30 days or 5 half-lives (whichever is longer) preceding the first dose of study medication.
14. History of prior use of or sensitivity to varenicline/Chantix®/Champix®.
15. Subjects who plan to move out of the area in the next year.
16. Subjects who are unwilling or unable to comply with the [Life Style Guidelines](#).
17. Other severe acute or chronic medical or psychiatric condition or laboratory abnormality that may increase the risk associated with trial participation or investigational product administration or may interfere with the interpretation of trial results and, in the judgment of the investigator, would make the subject inappropriate for entry into this trial.

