7.2.6. Actively Solicited Neuropsychiatric Adverse Events (Appendix 4)

The NAEI will be conducted at every clinic visit from baseline through Week 52. The Neuropsychiatric Adverse Event Interview (NAEI) must be conducted by a qualified mental health professional, who will actively inquire about the following type of adverse events: depression, anxiety, delusions, hallucinations, paranoia, psychosis, mania, panic, agitation, dissociative states, feeling abnormal, hostility, aggression and homicidal ideation. If a subject has a positive response to any item on the NAEI, a determination will be made by the investigator as to whether this meets criteria for an adverse event. If it does meet criteria as an adverse event it will be recorded on the adverse event pages of the Case Report Form. Dosing must be stopped if an adverse event moderate or severe in nature is elicited through this interview.

Hospital Anxiety and Depression Scale (HADS) (Appendix 3).

The Hospital Anxiety and Depression Scale (HADS) measures anxiety and depression in hospital and community settings and has also been validated in the adolescent outpatient population.¹⁷ It is a patient completed questionnaire that establishes the presence and severity of both anxiety (7 questions) and depression (7 questions) (Appendix 3).

The HADS is a self-report scale and contains 14 items rated on 4-point Likert-type scales. Two subscales assess depression and anxiety. The HADS will be completed by the subject at every clinic visit through Week 52. Dosing must be stopped if the HADS score for either depression or anxiety is ≥ 15 .

Subjects' self-report via the HADS is aimed to more fully characterize potential depression and anxiety related events. These additional measurements will be collected and evaluated in a different manner than the observed or volunteered adverse events. No attempt will be made to resolve any apparent discrepancies between observed or volunteered adverse events and the additional data collected from subjects using the HADS self-report. These additional data will be presented in separate tables, separate figures, and separate data listings, and will be reviewed in the final study report.

Adverse event incidence rates will not be calculated from the self-reported HADS data but rather from the spontaneously reported information, the NAEI and the CSSRS data described above, recorded on the adverse event pages from the Case Report Form (CRF).

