8.2.6.7. Hospital Anxiety and Depression Scale

The Hospital Anxiety and Depression Scale (HADS) measures anxiety and depression in hospital and community settings and has also been validated in the adolescent outpatient population. It is a patient completed questionnaire that establishes the presence and severity of both anxiety (7 questions) and depression (7 questions).

The baseline anxiety total score and depression total score as well as change from baseline at each visit will be summarized by treatment group as described in [Section 8.1.2.1](#). In addition the maximum increase in the anxiety total score and depression total score per subject while on treatment will be summarized by treatment group.

Shift tables for HADs Depression subscore and HADS Anxiety Subscore will be produced by treatment and stratum, as well as overall. The shift will be from baseline to the worst score post-baseline. Both baseline and post-baseline will be categorized to 0-7, 8-10, and 11+. The number and percent of patients who increased to a higher category will be tabulated as well.

If more than one question within a domain (anxiety or depression) is missing, the score will be set to missing. If only one question is missing, the missing response will be imputed with the domain-specific mean based on the remaining questions.

These will be summarized for the following groups:

- Overall study
- 12-16 year old age stratum
- 12-16 year old age stratum, ≤55 kg weight stratum
- 12-16 year old age stratum, >55 kg weight stratum
- 17-19 year old age stratum

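### The two HADS stopping rules disagree at a depression score of exactly 15: Section 7.2.6 stops the drug, while Section 6.4, the only section that requires referral, does not apply

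*Protocol*

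**What the plan says.** Two places in the protocol tie a HADS score to a mandatory action.

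- **Section 6.4 (Early Permanent Discontinuation of Study Drug).** The lead-in to the list is "A subject must be discontinued from study medication and referred for appropriate medical or psychiatric evaluation and follow-up if there is". The HADS item on that list is "A score ≥ 15 for anxiety or >15 for depression on the HADS". The other two items are any positive C-SSRS answer and an NAEI-elicited event graded moderate or severe.
- **Section 7.2.6 (HADS paragraphs).** "Dosing must be stopped if the HADS score for either depression or anxiety is ≥ 15". This section says nothing about referral.

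Three other places bear on the point. Exclusion criterion 8 in Section 4.2 bars anyone scoring 8 or more on either subscale. Section 7.2.6 describes the instrument: "The HADS is a self-report scale and contains 14 items rated on 4-point Likert-type scales", with seven items each for anxiety and depression. SAP Section 8.2.6.7 defines the shift-table groups: "Both baseline and post-baseline will be categorized to 0-7, 8-10, and 11" and above.

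**The concern.** A mandatory stopping rule should give one answer at every attainable score. Here it gives two answers for depression at 15. The protocol offers no reason for a looser limit on depression than on anxiety, although depressed mood and suicidality are among the harms Section 6.4 is written to catch.

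The gap runs in one direction. A site that stops at 15 breaches neither section. A site that uses the Section 6.4 list as its checklist could continue a subject whom Section 7.2.6 says must stop.

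Referral is the harder part, because reading the two sections together does not settle it. The stricter dosing rule comes from Section 7.2.6, but the duty to refer on a HADS score is stated only in Section 6.4. A fully compliant site must therefore refer at anxiety 15 and has no matching HADS-based duty at depression 15.

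The subjects are adolescents, at least 210 of the planned 300 are aged 12-16 (Section 9.1), and the trial is designated a post-authorization safety study with active neuropsychiatric monitoring.

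**Working it through.** The plan states no figure to reproduce. The check compares the two rules score by score.

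**Scale.** Each subscale has 7 items scored 0-3 (Appendix 3). The range is 7 × 0 = 0 to 7 × 3 = 21 in whole points, so 15 is attainable.

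**Rules side by side.**

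| Score | Section 6.4: stop and refer | Section 7.2.6: stop dosing |
|---|---|---|
| Anxiety ≤14 | no | no |
| Anxiety 15-21 | yes | yes |
| Depression ≤14 | no | no |
| **Depression 15** | **no** (15 > 15 is false) | **yes** (15 ≥ 15 is true) |
| Depression 16-21 | yes | yes |

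For depression, Section 6.4 covers 16-21 (6 values) and Section 7.2.6 covers 15-21 (7 values). The difference is the single value 15.

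**Clinical distance.** The highest eligible score is 7, so reaching 15 takes a rise of at least 15 − 7 = 8 points.

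**Where the decision arises.** HADS is scheduled at every visit from Week 1 to Week 12, and drug is dispensed through Week 11 (Table 1; Section 5.5). The stop-or-continue decision therefore arises at 11 visits per subject, at most 300 × 11 = 3,300 assessments. This is the number of occasions on which the rule is applied, not the number affected. HADS is also done at Week 12 and at nine follow-up clinic visits (Weeks 13-16, 20, 28, 36, 44 and 52). No drug remains to be stopped at those visits. If the Section 6.4 list is read as covering all clinic visits, it is the only HADS referral rule there, and it leaves out depression = 15.

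**Subjects affected.** The documents give no frequency for a depression score of 15. Assumed shares of the 300 subjects who ever score exactly 15 on drug give:

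- 0.3%: 0.003 × 300 = 0.9, about 1 subject
- 1%: 0.01 × 300 = 3 subjects
- 3%: 0.03 × 300 = 9 subjects

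These are upper figures for each assumption, because some of these subjects would also meet the C-SSRS or NAEI trigger.

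**Effect on the primary analysis.** The rule does not change. The Full Analysis Set is all randomized subjects (SAP 5.1), and the count-as-smoker rule depends on leaving the study, not on stopping the drug (SAP 5 and 7).

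**The case against.** The strongest reply is that Section 7.2.6 is unconditional. Section 6.4 does not permit dosing at 15; it only omits that score from a list. Continued dosing therefore requires a site to overlook a mandatory rule in the section that describes the HADS. This is correct, and it confines the dosing risk to sites that rely on Section 6.4 alone.

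There are also several backstops:

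- Section 6.4 asks that the C-SSRS, HADS and NAEI evaluations be done by an adolescent or pediatric psychiatrist. Sections 7.2.5 and 7.2.6 assign the C-SSRS and NAEI to a mental health professional at each clinic visit.
- Of subjects with symptoms such as depressed mood, Section 6.4 says: "A subject who experiences such events should stop dosing and immediately report any such symptoms to the study staff".
- Each site has an emergency plan with a psychiatrist available at all times.
- The NAEI asks about low mood, lost interest and crying. Under Section 8.8, any interference with usual function is enough to grade an event moderate, which is a low bar for stop and referral.

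These measures shrink the exposed group but do not close the gap. None is tied to a HADS depression score of 15, and an NAEI event graded mild triggers nothing. What remains is a subject at exactly 15 with no positive C-SSRS answer and nothing above mild on the NAEI, for whom no text requires referral.

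Two smaller objections have some force. The assumed frequencies have no basis in the documents, so the firm magnitude is one score of unknown frequency. The > could also be a ≥ that lost its lower bar when the text was converted. That is unlikely, since ≥ survives for anxiety in the same bullet, but the sponsor should check the source file. An authoring slip is plausible too: the amendment log records a symbol error introduced in Section 5.1 during formatting.

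**Conclusion.** The concern holds. The depression threshold in Section 6.4 is wrong as written: it conflicts with Section 7.2.6 at a score of 15 and leaves that score without HADS-triggered referral even where both sections are followed. The SAP's HADS groups are for tabulation and do not settle the matter.

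The defect is narrow: one of 22 attainable scores (0 to 21) on one subscale. The 1-to-9-subject range rests entirely on the assumed 0.3% to 3%. The point matters because the rule protects minors and 15 lies well above the entry limit. Efficacy inference is untouched.

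**What to change.** In Section 6.4, change the HADS item to ≥15 for anxiety or ≥15 for depression, so that both the stop and the referral apply at 15. Add a cross-reference in Section 7.2.6 to the Section 6.4 referral requirement, so that a reader of either section finds both duties. Issue the change to sites by clarification letter or amendment.

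The essential change is one character. It needs no extra visits, data or subjects. The one downside is that a few subjects scoring exactly 15 on depression may stop drug who would otherwise have continued. Section 6.4 already allows them to stay in follow-up.
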